## 2 List of Abbreviations and Glossary of Terms

Abbreviation	Definition
ADaM	Analysis data model
AE	Adverse event
AESI	Adverse event of special interest
ALT	Alanine aminotransferase
ANA	Antinuclear antibody
AST	Aspartate aminotransferase
ATC	Anatomical Therapeutic Chemical
AUC	Area under the concentration-time curve
BDRM	Blinded data review meeting
BMI	Body mass index
BUN	Blood urea nitrogen
C max	Maximum concentration
C trough	Trough concentration
CDASI	Cutaneous Dermatomyositis Disease Area and Severity Index
CI	Confidence interval
CK	Creatine kinase
CSM	Core set measure
CSR	Clinical study report
DAT	Direct antiglobulin test
HAQ-DI	Health Assessment Questionnaire - Disability index
DM	Dermatomyositis
DOW	Definition of worsening
DVT	Deep vein thrombosis
ECG	Electrocardiogram
eCOA	Electronic clinical outcomes assessment
eCRF	Electronic case report form
EOP1	End of Study Period 1
EOP2	End of Study Period 2
EOP3	End of Study Period 3
EQ-5D-5L	EuroQol 5-Dimension 5-Level Questionnaire

Abbreviation	Definition
EULAR/ACR	European League Against Rheumatism / American College of Rheumatology
GGT	Gamma glutamyl transferase
HAQ	Health Assessment Questionnaire
HBV	Hepatitis B virus
HCV	Hepatitis C virus
HIV	Human immunodeficiency virus
IDMC	Independent data monitoring committee
IgG	Immunoglobulin G
IMACS	International Myositis Assessment and Clinical Studies Group
IMP	Investigational medicinal product
IRT	Interactive response technology
ITT	Intent-to-Treat
LDH	Lactate dehydrogenase
LS-mean	Least square mean
MAA	Myositis-associated autoantibodies
MAR	Missing at random
MDAAT	Myositis Disease Activity Assessment Tool
MedDRA	Medical Dictionary for Regulatory Activities
mITT	modified Intent-to-Treat analysis set
mITT-Ex	modified Intent-to-Treat analysis set extended
MMRM	Mixed Model Repeated Measures
MMT-8	Manual muscle testing of 8 muscle groups
MSA	Myositis-specific autoantibodies
PE	Pulmonary embolism
PK	Pharmacokinetics
PM	Polymyositis
PP	Per Protocol analysis set
PT	Preferred term
SAE	Serious adverse event
SAF	Safety analysis set
SAF-Ex	Safety analysis set extended

Abbreviation	Definition
SAF-P3	Safety analysis set for Study Period 3
SAP	Statistical analysis plan
SC	Subcutaneous
SCR	Screened Analysis Set
SMQ	Standard MedDRA query
SOC	System organ class
TEAE	Treatment-emergent adverse event
TEE	Thromboembolic event
TIS	Total improvement score
TSQM-9	Abbreviated Treatment Satisfaction Questionnaire for Medication
ULN	Upper limit of normal
UNS	Unscheduled visit
VAS	Visual analog scale
WHO-DDE	World Health Organization - Drug Dictionary Enhanced
WPAI-GH	Work Productivity and Activity Impairment Questionnaire for General Health

## Glossary of Terms

Term	Definition
Definition of Worsening (DOW)	
The DOW consists of meeting 1 of the following 3 criteria on 2 consecutive study visits at least 2 weeks apart:
 
 
• Physician Global Activity Assessment Visual Analog Scale (VAS) worsening <math>\geq 2</math> cm* and Manual Muscle Test (MMT-8) worsening <math>\geq</math> absolute 10%, OR
 
• Extramuscular Global Assessment worsening <math>\geq 2</math> cm on the Myositis Disease Activity Assessment Tool (MDAAT) VAS, OR
 
• Any 3 of 6 core set measures (CSM) worsening by <math>\geq</math> absolute 20%
 
 
* If baseline Physician Global VAS is 8 to 10, then any worsening on Physician Global VAS is acceptable as long as MMT-8 criterion is met.

EOP	End of Period distinguishes periods 1, 2 and 3 of the study.

Term	Definition
g/kg	Investigational medicinal product (IMP) dose throughout the study will be calculated by g/kg of body weight. For all dosing references, the dose description is shortened to g/kg.
Primary data analysis	The primary data analysis (ie. EOP1 analysis) includes all data collected during Study Period 1.
Primary endpoint analysis	The primary endpoint analysis refers to the analysis of the primary objective, ie, the responder status based on the TIS assessments at Weeks 17, 21, and 25 (see Section 10.2)
Protocol violation	Major protocol deviation (ie, a deviation that could have a significant effect on the subject's safety, rights, or welfare and / or on the integrity of the study data)
Responder	
A subject with a Total Improvement Score (TIS) <math>\geq 20</math> points at Week 25 and at least at one of the previous scheduled visits (Week 17 or Week 21), who completes 24 weeks of randomized IMP treatment without the use of oral rescue corticosteroid treatment
 
Note: for subjects who discontinue from IMP or the study for reasons that are related to the Ukraine war before Week 25, a multiple imputation approach will be used for dealing with missing TIS values (see Section 10.2).

Study treatment	Refers to IMP
Subject eligible for continuing treatment in Study Period 3	At the Week 53 Visit, subjects may continue to the Study Period 3 if eligible. The basis for eligibility is a TIS $\geq 20$ points at the Week 49 Visit. Subjects who continue the study will receive open-label IgPro20 0.5 g/kg SC infusions weekly in Study Period 3.
Treatment Sequence	
Sequence A: 0.5 g/kg IgPro20 for 24 weeks (Study Period 1) followed by 0.5 g/kg IgPro20 for 28 weeks (Study Period 2)
 
Sequence B: placebo for 24 weeks (Study Period 1) followed by 0.5 g/kg IgPro20 for 28 weeks (Study Period 2)
 
After completing Study Period 2, eligible subjects may continue treatment with SC infusions of IgPro20 0.5 g/kg in Study Period 3.

Oral concomitant corticosteroid treatment	Includes both oral rescue and concomitant corticosteroid treatment

### 3 Purpose

This statistical analysis plan (SAP) provides a detailed and complete description of the planned statistical analyses for the following analyses to be presented in Clinical Study Reports (CSRs):

- primary data analysis of the study IgPro20\_3007 including all data collected during Study Period 1 (EOP1 analysis) will be done after all subjects have completed all assessments for Study Period 1
- at the time of the EOP1 analysis additional adverse event, efficacy data, and pharmacokinetic data of Study Period 2 will be analyzed. Efficacy analysis of the Study Period 2 data will be restricted to all subjects completing or discontinuing prematurely Study Period 2 at the time of data cut-off for the EOP1 analysis; the adverse events analysis will include all subjects treated in any study period at the time of data cut-off for EOP1 analysis; the pharmacokinetic analysis will include all subjects who have completed the rich PK sampling at Week 37. The respective analyses will be based on cleaned data.
- EOP2 analysis will be done after all subjects have completed all assessments for Study Period 2.
- EOP3 analysis will be done after all subjects have completed all assessments for Study Period 3.

Mock tables, listings, and figures shells are provided in separate supporting documents.

This SAP complies with the International Conference on Harmonisation (ICH) Harmonised Tripartite Guideline Topic E9, Statistical Principles for Clinical Trials. It is based upon the following study documents:

- Study Protocol Amendment 4, (dated 20 October 2022)

All decisions regarding the primary data analysis of the study results, as defined in this SAP document, must be made prior to unblinding of the study data.

## 4 Study Design

### 4.1 Study Design

This is a phase 3, multicenter, randomized, placebo-controlled, double-blind study of IgPro20 (subcutaneous immunoglobulin G [SCIG]) treatment in adult subjects with DM with or without muscle weakness.

This study consists of Screening and 3 treatment periods:

[figure not shown]
- Screening Period: Up to 2 months during which screening assessments must be completed
- Study Period 1: 24 weeks of either IgPro20 or placebo administration
- Study Period 2: 28 weeks of IgPro20 administration
- Study Period 3: additional treatment with open-label IgPro20 for subjects who have shown treatment benefit at Week 53

After Screening, subjects will be randomly assigned (1:1) to 1 of 2 sequences of double-blind weekly IMP treatment (0.5 g/kg IgPro20 and placebo). Subjects assigned to **Sequence A** will receive 0.5 g/kg IgPro20 for 24 weeks (Study Period 1) followed by 0.5 g/kg IgPro20 for 28 weeks (Study Period 2). Subjects assigned to **Sequence B** will receive placebo for 24 weeks (Study Period 1) followed by 0.5 g/kg IgPro20 for 28 weeks (Study Period 2).

The study data will be unblinded for the primary data analysis (ie, end of Study Period 1 [EOP1] analysis) after all subjects have completed all assessments for Study Period 1 and the data has been cleaned for primary data analysis. Subjects and caregivers, as well as site personnel involved in the conduct of the study, will remain blinded to treatment allocation until all subjects have completed all assessments for Study Period 2.

At the Week 53 Visit, subjects may be eligible to continue to Study Period 3 if their TIS was  $\geq$  20 points at the Week 49 Visit. In Study Period 3 subjects will receive open-label IgPro20 0.5 g/kg subcutaneous (SC) infusions weekly until the end of the study (see CSP Section 3.7).

The primary objective of this study is to assess the efficacy of IgPro20 0.5 g/kg weekly subcutaneous doses in comparison to placebo in adult subjects with DM, as measured by responder status based on TIS assessments at Weeks 17, 21, and 25.

**Figure 1: Study Design**

Abbreviations: DM = dermatomyositis; DOW = Definition of Worsening; EOP = end of Study Period; TIS = Total Improvement Score.

## 4.2 Objectives and Endpoints

The primary objective of this study is to assess the efficacy of IgPro20 0.5 g/kg weekly SC doses in comparison to placebo in adult subjects with DM, as measured by responder status based on the TIS assessments at Weeks 17, 21, and 25.

The secondary objectives of the study are:

1. To assess the efficacy, with additional clinical outcome measures, of IgPro20 in comparison to placebo
2. To assess the safety of IgPro20 in comparison to placebo
3. To assess the safety and efficacy of IgPro20 at Week 53
4. To assess the safety of IgPro20 from after completion of Week 53 to the end of study participation

**Table 1: Study Objectives, Endpoints and Summary Measures for Primary and Secondary Endpoints**

Objectives	Endpoints	Summary Measure(s)
Primary	Responder status based on the TIS assessments at Weeks 17, 21, and 25	
 
Point estimate and 95% confidence interval (CI) for the responder rate by treatment sequence
 
Point estimate and 95% CI for the odds ratio (IgPro20:placebo)
 

Key Secondary		
1	TIS at Week 25	
 
Mean TIS values at Week 25 by treatment sequence
 
Point estimates and 95% CI for mean difference (IgPro20 – placebo) at Week 25
 

1	Change from Baseline in MMT-8 (Manual Muscle Testing of 8 muscle groups) at Week 25	
 
Mean changes from Baseline in MMT-8 at Week 25 by treatment sequence
 
Point estimates and 95% CI for mean change difference (IgPro20 – placebo) at Week 25
 

1	Change from Baseline in Cutaneous Dermatomyositis Disease Area and Severity Index (CDASI) total activity score at Week 25	
 
Mean changes from Baseline in CDASI total activity score at Week 25 by treatment sequence
 
Point estimates and 95% CI for mean change difference (IgPro20 – placebo) at Week 25
 

1	Reduction of oral corticosteroid dose at Week 25	
 
Point estimate and 95% CI of subjects who are able to reduce the oral corticosteroid dose by <math>\geq 25\%</math> at Week 25 by treatment sequence
 
Point estimates and 95% CI for the odds ratio (IgPro20:placebo) at Week 25
 

Objectives	Endpoints	Summary Measure(s)
Secondary Efficacy		
1, 3	TIS from Week 5 to Week 53	
 
Mean TIS by treatment sequence at each visit
 
Percentage of subjects achieving TIS <math>\geq 20</math>, <math>\geq 40</math>, and <math>\geq 60</math> points by treatment sequence at each visit
 
Time to first achieving TIS <math>\geq 20</math>, <math>\geq 40</math>, and <math>\geq 60</math> points by treatment sequence
 
Percentage of subjects achieving TIS <math>\geq 20</math> points at the end of the Study Period 2
 

1, 3	Individual core set measures (CSMs; except muscle enzyme) and CDASI from Baseline to Week 53	
 
Mean changes from Baseline by treatment sequence between Week 5 and Week 25
 
Mean changes from Week 25 by treatment sequence between Week 29 and Week 53
 
 
Individual CSMs include:
 
 
Physician Global Disease Activity
 
Patient Global Activity Assessment
 
MMT-8
 
Health Assessment Questionnaire – Disability Index
 
Extramuscular Global Assessment
 

Objectives	Endpoints	Summary Measure(s)
1, 3	Definition of Worsening (DOW) from Baseline to Week 53	
 
Number and percentage of subjects meeting DOW at least once, twice, or <math>></math> twice by treatment sequence
 
Time to meeting DOW for the first time by treatment sequence
 
Number and percentage of subjects meeting DOW and receiving rescue corticosteroid treatment by treatment sequence
 

1	Reduction of oral concomitant corticosteroid dose from Baseline to Week 53	
 
Number and percentage of subjects who start oral concomitant corticosteroid dose taper before Week 25 by treatment sequence
 
Number and percentage of subjects who are able to reduce their oral concomitant corticosteroid dose by <math>\geq 25\%</math>, <math>\geq 50\%</math>, and <math>\geq 75\%</math> by Week 25 or by Week 53 by treatment sequence
 

3	Use of rescue corticosteroid treatment from Baseline to Week 25	
 
Percentage of subjects receiving rescue corticosteroid treatment by treatment sequence
 
Percentage of subjects whose rescue corticosteroid treatment is tapered by treatment sequence
 
Time to first administration of rescue corticosteroid treatment
 

Objectives	Endpoints	Summary Measure(s)
1, 3	Mobility, Self-care, and Usual Activities domains of EuroQoL 5-Dimension Questionnaire (EQ-5D-5L) from Baseline to Week 53	
 
Number and percentage of subjects having at least 1 level, 2 levels, and > 2 levels of improvement from Baseline by treatment sequence at Week 13 and Week 25
 
Number and percentage of subjects having no reduction in levels, at least 1 level, 2 levels, and > 2 levels of improvement from Week 25 by treatment sequence at Week 41 and Week 53
 

Secondary Safety		
2,3,4	Treatment-emergent adverse events (TEAEs)	
 
Percentage of subjects with TEAEs
 
Percentage of subjects with related TEAEs
 
Percentage of subjects with serious TEAEs
 
Rate of TEAEs per time at risk
 
Rate of mild, moderate, and severe TEAEs per time at risk
 
Rate of related TEAEs per time at risk
 
Rate of serious TEAEs per time at risk
 

**Table 2: Study Objectives and Endpoints for Exploratory Endpoints**

Objectives	Endpoints
Exploratory: Study Period 1 and Study Period 2 (From Baseline to Week 53)	
• To assess pain / discomfort and anxiety / depression domains of EQ-5D-5L	• Pain / discomfort and anxiety / depression domains of EQ-5D-5L
• To assess Work Productivity and Activity Impairment Questionnaire for General Health (WPAI-GH)	• WPAI-GH
• To assess Abbreviated Treatment Satisfaction Questionnaire for Medication (TSQM-9)	• TSQM-9
• To assess Timed Up and Go result for functional ability to rise from a chair and ambulate	• Timed Up and Go
• To assess itch (pruritus)	• 5-Dimension (5-D) Itch (pruritus) score
• To assess muscle enzymes	• Creatine kinase (CK) • Lactate dehydrogenase (LDH) • Aspartate aminotransferase (AST) • Alanine aminotransferase (ALT) • Aldolase
• To assess the pharmacokinetics (PK) of IgG in Week 37	• Serum IgG PK parameters
• To assess antinuclear antibodies (ANA) and myositis-specific autoantibodies (MSA) and myositis-associated autoantibodies (MAA)	• ANA, MSA, and MAA
Exploratory: Study Period 3 (After Week 53)	
• To assess the efficacy of IgPro20 from after completion of Week 53 to the end of study participation	• Physician Global Disease Activity, Patient Global Activity Assessment, MMT-8, HAQ-DI, and CDASI from Baseline to EOP3
• To assess quality of life of IgPro20 from after completion of Week 53 to the end of study participation	• Mobility, Self-care, and Usual Activities domains of EuroQol 5-Dimension Questionnaire (EQ-5D-5L) from Baseline to EOP3
• Use of corticosteroid treatment from Week 53 to the end of study participation	• Reduction of average daily dose

#### 4.2.1 Primary Study Hypothesis

The primary study objective is to test the superiority of IgPro20 relative to placebo. The study is designed with the objective of testing the null and the alternative hypotheses for the responder rates as defined below:

$$H_{01}: \pi_{\text{IgPro20}} \leq \pi_{\text{Pbo}} \quad \text{vs.} \quad H_{11}: \pi_{\text{IgPro20}} > \pi_{\text{Pbo}}$$

where  $\pi_{\text{IgPro20}}$  and  $\pi_{\text{Pbo}}$  represent the responder rates with IgPro20 and placebo, respectively. Under the null hypothesis, the assumption is that no beneficial effect is afforded by IgPro20 while the alternative hypothesis states that IgPro20 is effective in increasing the responder rate compared to the placebo arm.

Statistical significance will be assessed using the one-sided alpha level of 0.025.

#### 4.2.2 Key Secondary Endpoints Hypotheses

In addition to the primary study hypotheses, four hypotheses are tested to show the superiority of IgPro20 relative to placebo on key secondary endpoints:

$$H_{02}: \text{TIS}\mu_{\text{IgPro20}} \leq \text{TIS}\mu_{\text{Pbo}} \quad \text{vs.} \quad H_{12}: \text{TIS}\mu_{\text{IgPro20}} > \text{TIS}\mu_{\text{Pbo}}$$

$$H_{03}: \text{MMT}\mu_{\text{IgPro20}} \leq \text{MMT}\mu_{\text{Pbo}} \quad \text{vs.} \quad H_{13}: \text{MMT}\mu_{\text{IgPro20}} > \text{MMT}\mu_{\text{Pbo}}$$

$$H_{04}: \text{CDASI}\mu_{\text{IgPro20}} \geq \text{CDASI}\mu_{\text{Pbo}} \quad \text{vs.} \quad H_{14}: \text{CDASI}\mu_{\text{IgPro20}} < \text{CDASI}\mu_{\text{Pbo}}$$

$$H_{05}: \text{Cort}\pi_{\text{IgPro20}} \leq \text{Cort}\pi_{\text{Pbo}} \quad \text{vs.} \quad H_{15}: \text{Cort}\pi_{\text{IgPro20}} > \text{Cort}\pi_{\text{Pbo}}$$

Where

- $\text{TIS}\mu_{\text{IgPro20}}$  and  $\text{TIS}\mu_{\text{Pbo}}$  represent the mean TIS in IgPro20 and placebo at Week 25,
- $\text{MMT}\mu_{\text{IgPro20}}$  and  $\text{MMT}\mu_{\text{Pbo}}$  represent the mean change from baseline in MMT-8 in IgPro20 and placebo at Week 25, and
- $\text{CDASI}\mu_{\text{IgPro20}}$  and  $\text{CDASI}\mu_{\text{Pbo}}$  represent the mean change from baseline in CDASI total activity score in IgPro20 and placebo at Week 25,
- $\text{Cort}\pi_{\text{IgPro20}}$  and  $\text{Cort}\pi_{\text{Pbo}}$  represent the proportion of subjects who are able to reduce the oral concomitant corticosteroid dose by at least 25% in IgPro20 and placebo at Week 25.

Issues related to multiplicity arising from testing the primary endpoint and key secondary endpoints will be addressed using the serial gatekeeping procedure [Dmitrienko et al, 2013] to control the overall family error rate at a one-sided significance level of 0.025. Two families of null hypotheses are defined with family 1 consisting of the primary endpoint ( $H_{01}$ ) and family 2 consisting of the 4 key secondary endpoints ( $H_{02}$ ,  $H_{03}$ ,  $H_{04}$ , and  $H_{05}$ ).

The general process flow of the hypothesis testing is as follows: the null hypothesis associated with the primary endpoint  $H_{01}$  will be tested first. If and only if the resulting one-sided p-value is  $\leq 0.025$ , testing of  $H_{02}$ ,  $H_{03}$ ,  $H_{04}$ , and  $H_{05}$  will be undertaken; otherwise, further hypothesis testing will cease and  $H_{02}$  through  $H_{05}$  will be retained.

After  $H_{01}$  is rejected, the hypothesis tests associated with key secondary endpoints will be performed using the Hommel step-up procedure at a one-sided significance level of 0.025. The resulting p-values of the second family are ordered from the smallest to the largest,  $P_{(1)}$ ,  $P_{(2)}$ ,  $P_{(3)}$ , and  $P_{(4)}$  with the associated ordered null hypotheses  $H_{(1)}$ ,  $H_{(2)}$ ,  $H_{(3)}$ , and  $H_{(4)}$ . The Hommel step-up procedure is described below:

- Step 1: start with the largest p-value  $P_{(4)}$ . If  $P_{(4)} \leq 0.025$ , reject all null hypotheses in the family,  $H_{(1)}$ ,  $H_{(2)}$ ,  $H_{(3)}$ , and  $H_{(4)}$ . Otherwise, fail to reject  $H_{(4)}$  and proceed to Step 2.
- Step 2: test the null hypothesis  $H_{(3)}$  associated with the p-value  $P_{(3)}$ . If  $P_{(3)} \leq 0.0125$ , reject  $H_{(1)}$ ,  $H_{(2)}$ , and  $H_{(3)}$ . Otherwise, fail to reject  $H_{(3)}$  and proceed to Step 3.
- Step 3: test the null hypothesis  $H_{(2)}$  associated with the p-value  $P_{(2)}$ . If  $P_{(2)} \leq 0.00833$ , (or  $P_{(3)} \leq 0.01667$  and  $P_{(2)} \leq 0.0125$ ) reject  $H_{(1)}$  and  $H_{(2)}$ . Otherwise, fail to reject  $H_{(2)}$  and proceed to the last step, Step 4.
- Step 4: test the null hypothesis  $H_{(1)}$  associated with the smallest p-value  $P_{(1)}$ . If  $P_{(1)} \leq 0.00625$ , or  $P_{(1)} \leq 0.00833$  and  $P_{(2)} \leq 0.0125$ , or  $P_{(1)} \leq 0.00833$  and  $P_{(3)} \leq 0.01875$  reject the null hypothesis  $H_{(1)}$ . Otherwise, fail to reject  $H_{(1)}$ .

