- Step 3: test the null hypothesis  $H_{(2)}$  associated with the p-value  $P_{(2)}$ . If  $P_{(2)} \leq 0.00833$  (or  $P_{(3)} \leq 0.01667$  and  $P_{(2)} \leq 0.0125$ ), reject  $H_{(1)}$  and  $H_{(2)}$ . Otherwise, fail to reject  $H_{(2)}$  and proceed to the last step, Step 4.
- Step 4: test the null hypothesis  $H_{(1)}$  associated with the smallest p-value  $P_{(1)}$ . If  $P_{(1)} \leq 0.00625$ , or  $P_{(1)} \leq 0.00833$  and  $P_{(2)} \leq 0.0125$ , or  $P_{(1)} \leq 0.00833$  and  $P_{(3)} \leq 0.01875$ , reject the null hypothesis  $H_{(1)}$ . Otherwise, fail to reject  $H_{(1)}$ .

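### Step 4 of the written Hommel procedure omits a rejection condition, so the stated rule can retain a key secondary hypothesis that Hommel rejects

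*SAP*

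**What the plan says.** SAP Section 4.2.2 sets up serial gatekeeping "to control the overall family error rate at a one-sided significance level of 0.025". The primary hypothesis is tested first. If it is rejected, testing moves to "family 2 consisting of the 4 key secondary endpoints", and those tests "will be performed using the Hommel step-up procedure at a one-sided significance level of 0.025". The p-values are ordered P(1) ≤ P(2) ≤ P(3) ≤ P(4), and the steps are, in summary:

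- Step 1: if P(4) ≤ 0.025, reject all four.
- Step 2: otherwise, if P(3) ≤ 0.0125, reject H(1) to H(3).
- Step 3: otherwise, if P(2) ≤ 0.00833, or if P(3) ≤ 0.01667 and P(2) ≤ 0.0125, reject H(1) and H(2).
- Step 4: otherwise, reject H(1) if P(1) ≤ 0.00625; or if P(1) ≤ 0.00833 and P(2) ≤ 0.0125; or under the last alternative, "or $P_{(1)} \leq 0.00833$ and $P_{(3)} \leq 0.01875$ reject the null hypothesis". If none applies, H(1) is retained.

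Protocol Section 10.4.2.4.4 prints the same three Step 4 alternatives. No other section of either document adds a further one.

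**The concern.** No Step 4 alternative allows rejection when P(1) lies between 0.00833 and 0.0125. Step 3 does use the pairing of an α/2 threshold with P(3) ≤ 0.01667 for H(2), but Step 4 does not carry it over to H(1). If Hommel needs it there, the plan names one procedure and writes out a slightly weaker one.

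At stake is a confirmatory claim. In the affected region the choice of rule decides between one successful key secondary endpoint and none. SAP Section 3 requires decisions on the primary data analysis to be made before unblinding, and the plan does not say whether the name or the steps govern. The tipping point analysis in SAP Section 10.4.1 takes its entry condition and its stopping level from Section 4.2.2, so it inherits the ambiguity.

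**Working it through.** **Inputs.** Four hypotheses, one-sided α = 0.025, and the four steps, all from SAP Section 4.2.2 (the same in protocol Section 10.4.2.4.4).

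**The plan's constants reproduce.** α/4 = 0.00625; α/3 = 0.00833; α/2 = 0.0125; 2α/3 = 0.01667; 3α/4 = 0.01875. The fault is a missing branch and not a wrong constant.

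**What Hommel requires at Step 4.** Hommel is equivalent to closed testing with Simes tests: H(1) is rejected only if every intersection containing it is rejected. A Simes test on m hypotheses rejects if the i-th smallest p-value is ≤ iα/m for some i. At Step 4, P(4) > α, which leaves three binding requirements:

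- {1,4}: P(1) ≤ α/2.
- {1,3,4}: P(1) ≤ α/3, or P(3) ≤ 2α/3.
- {1,2,3,4}: P(1) ≤ α/4, or P(2) ≤ α/2, or P(3) ≤ 3α/4.

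The other intersections containing H(1) follow from these because P(2) ≤ P(3). Two cases satisfy all three:

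1. P(1) ≤ α/3, together with one of the three options in the last line. These are exactly the three alternatives printed in Step 4.
2. P(1) ≤ α/2 and P(3) ≤ 2α/3. The last line then holds automatically, because 2α/3 < 3α/4. This is **P(1) ≤ 0.0125 and P(3) ≤ 0.01667**, and it is not printed.

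**Where it matters.** If P(1) ≤ 0.00833, the third printed alternative already covers case 2. If P(2) ≤ 0.0125, Step 3 has already rejected. The rules therefore differ only when

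0.00833 < P(1) ≤ 0.0125 < P(2) ≤ P(3) ≤ 0.01667 and P(4) > 0.025.

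**Worked case, p = (0.010, 0.013, 0.016, 0.20).** Written steps:

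- Step 1 fails: 0.20 > 0.025.
- Step 2 fails: 0.016 > 0.0125.
- Step 3 fails: 0.013 > 0.00833 and 0.013 > 0.0125.
- Step 4 fails: 0.010 > 0.00833, so no alternative applies.

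Nothing is rejected. The Hommel-adjusted p-value for H(1) is the largest Simes p-value over the intersections containing it:

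- {1,2,3,4}: min(4 × 0.010, 2 × 0.013, 4/3 × 0.016, 0.20) = 0.0213
- {1,3,4}: min(3 × 0.010, 1.5 × 0.016, 0.20) = 0.024
- {1,2,4}: min(3 × 0.010, 1.5 × 0.013, 0.20) = 0.0195
- {1,4}: min(2 × 0.010, 0.20) = 0.020

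{1,2,3}, {1,2}, {1,3} and {1} give nothing larger than 0.020. The maximum is 0.024 ≤ 0.025, so Hommel rejects H(1). The four adjusted p-values are 0.024, 0.026, 0.032 and 0.20, as a standard Hommel routine also returns.

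**Numerical check.** Over 60,000 p-value vectors drawn close to the thresholds, with unrounded constants, the written steps and closed Simes testing disagreed 401 times. Each time Hommel rejected one hypothesis and the written steps none. With the fourth alternative added there were no disagreements. Because the draws were concentrated near the thresholds, 401 in 60,000 is not a probability of occurrence.

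**Probability of landing in the region.** The documents give no effect sizes or correlations for the key secondary endpoints, so these are assumptions: normal test statistics with equal correlation, given that the primary gate has been passed.

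| Mean z | Correlation | Probability |
|---|---|---|
| 2.2 to 2.5 on three endpoints (0 on the fourth), or 2.2 on all four | 0 to 0.7 | about 0.04% to 0.10% |
| 2.0 to 2.5 on three or four endpoints | 0 to 0.9 | about 0.04% to 0.2% |
| 3.0 on all four endpoints | 0 to 0.5 | about 0.01% to 0.04% |

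The 0.2% figure arises only at correlation 0.9.

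**The case against.** The strongest reply concerns weight. The region is narrow, is reached only after the primary test succeeds, costs at most one key secondary claim and errs on the conservative side. The steps are explicit and the same in both documents, so a reader could take them as the operative rule and Hommel as a loose label. Neither document names software for this test, so a conflict between software and text is hypothetical.

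The points on size and direction stand. The argument that the steps simply govern is weaker. The text presents them as a description of Hommel, and Steps 3 and 4 contain alternatives that the simpler Hochberg procedure lacks, so the evident intention was full Hommel. A deterministic rule that contradicts its own name still leaves the question of which one applies.

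A second objection is correct but tiny. The printed 0.01667 is rounded up from 0.016667, so the statement that the written rule only loses rejections holds exactly only for unrounded thresholds. At p = (0.010, 0.0125, 0.016668, 0.2) the printed Step 3 rejects two hypotheses, while Hommel rejects none: 1.5 × 0.016668 = 0.025002 > 0.025. SAP Section 7 reports these p-values to six decimals, so the difference would be visible. A correction using the same rounded constant would repeat the discrepancy.

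**Conclusion.** The concern holds. As written in both documents, Step 4 is not the Hommel procedure: it omits rejection of H(1) when P(1) ≤ α/2 and P(3) ≤ 2α/3. Steps 1 to 3 and the three printed Step 4 alternatives are correct apart from rounding. This follows from the definition of the procedure and needs no assumption about the data.

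Only the probability of occurrence rests on assumptions. It is about 0.04% to 0.2% for mean z of 2.0 to 2.5 on three or four endpoints with correlation up to 0.9. Rounding aside, the error is conservative, family-wise error is not inflated, and the primary endpoint is unaffected. This is a correction that should be made to a confirmatory decision rule, with small practical weight.

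**What to change.** Before unblinding for the primary data analysis, make one of two changes in SAP Section 4.2.2 and protocol Section 10.4.2.4.4:

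1. Add a fourth alternative to Step 4: or P(1) ≤ α/2 and P(3) ≤ 2α/3 (0.0125 and 0.01667 in the plan's notation). Writing all thresholds in the steps as fractions of α = 0.025 would also remove the rounding discrepancy.
2. Delete the written steps and state that Hommel-adjusted one-sided p-values from validated software are compared with 0.025. This is the cleaner option, since it leaves a single rule and no rounded constants.

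The cost is one clause or one sentence in each document. Nothing changes in data collection, sample size or the endpoint models. With unrounded thresholds or adjusted p-values, the family-wise error rate is that of the Hommel procedure already named.
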